c. Intent to Treat / Dropouts and Missing Data: The primary analyses in this study will be on the intentto treat (ITT) sample, i.e. on all randomized patients. If patients drop out of the study, they will be regarded as relapsed in the primary outcome analysis. This seems a safe assumption as it seems most likely dropouts will relapse. Cannabis consumption and cannabis abstinence, are assessed repeatedly over time and we will try to collect them at all study assessment points. We will account for unobserved data in secondary outcome variables using longitudinal mixed effects models (MEM) (Brown and Prescott 1999, Diggle et al. 2002) using PROC GLIMMIX in SAS[®]. MEMs do not require complete measurements data to estimate the outcome variable. The inferences from analyses with missing data are valid provided that they are "missing at random" (Little & Rubin, 2002). 'Missing at random' (i.e. the missing mechanism does not depend on the value of the unobserved outcome) is un-testable in most medical research and in our study as well. One can assume either parametric or semi-parametric models for the missingness that does depend on the unobserved outcome value and do the analysis (Diggle and Kenward 1994, Kenward 1998, Rotnitzky et al. 1998, Liu et al. 1999, Scharfstein et al. 1999). Comparison of the inferences from assuming various models for the missingness provides a measure of the validity of the efficacy estimate from the model that assumes missing 'at random'. One can also compute a local sensitivity index which measures the change in the estimated treatment effect in a neighborhood of the 'missing at random' model for missingness (Rotnitzky et al. 2001). We plan to perform a sensitivity analysis based on these two approaches to assess the effect of the assumption of missing 'at random' on the inference.

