Hypothesis 2: Nabilone and XR-NTX will significantly promote abstinence from cannabis use as compared to placebo during the final 2 weeks of study (weeks 11 and 12). The following logistic regression model will be used: (2) logit(Yij = 1) = $\beta 0 + \beta 1$ Ij + $\beta 2$ Uij + ϵ ij where Yij is a dichotomous measure indicating whether the i th subject in the treatment group j has used cannabis during the final 2 weeks of study, with Yij = 1 for non-abstinent and Yij = 0 for abstinent during the final 2 weeks of study; Uij is the vector of all appropriate covariates; Ij is the indicator variable for treatment with nabilone and XR-NTX; and ϵ ij is a random error term. Significant Ij indicates that the odds of abstinence from cannabis during the final 2 weeks are different in each group.

Hypothesis 3: Nabilone and XR-NTX will significantly increase time to dropout as compared to placebo. To test the secondary hypothesis 3, we will use the same model as in (1) to test whether retention is different between the two groups.

Hypothesis 4: Over time, the days of weekly cannabis use will be significantly less in the Nabilone and XR NTX group as compared to the placebo group. This hypothesis will be tested using the following

longitudinal mixed effects model: (3) Yijt = $\beta 0 + \beta 11j + \beta 2t + \beta 3t^*1j + \beta 4Uij + sij + \epsilon ijt$ where Y ijt is the days of cannabis used over a one-week period by the i th subject in the treatment group j at week t (t =1, 2, ..., 12); Uij is the vector of covariates; Ij is the indicator variable for treatment with nabilone and XR-NTX; sij is a random intercept for subject i and ϵijt is a random error term. Significant interaction t*Ij indicates that the effect of each treatment group is different over time (that corresponds to rejecting null hypothesis that $\beta 3= 0$). If so, the effect of time will be estimated for each group separately and the groups will be compared (using contrast) in the last time point t=12. If the interaction term is not significant (i.e., the difference between the treatment arms does not change over time), we will refit the model without the interaction term and test the significance of the main effect of treatment (i.e. rejecting the null hypothesis that $\beta 1 = 0$).

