Hypothesis 5: Over time, subjects in the nabilone and XR-NTX group will experience significant reduction in the pattern of cannabis withdrawal symptoms (measured as mean Marijuana Withdrawal Checklist score per week) compared to the subjects in the placebo group.

Hypothesis 6: Over time, subjects in the nabilone and XR-NTX group will exhibit significantly reduced cannabis cravings (as measured by Marijuana Craving Questionnaire) compared to subjects in the placebo group.

Hypothesis 7: Over time, subjects in the nabilone and XR-NTX group will experience significantly less sleep disturbance (as measured by the Medical Outcomes Study Sleep scale) compared to subjects in the placebo group. To test the secondary hypotheses 5, 6, and 7 we will use the same model as in (3) where Yijt is the appropriate outcome variable (as specified for each hypothesis) for the i th subject in the treatment group j at week t (t =1, 2, ..., 12). We will first test the interaction effect of group and time as described for Hypothesis 4.

iii. Exploratory Analyses We will explore whether there are differences between the two groups with respect to the number of adverse effects, side effects, and tolerability in relation to the primary outcome. We will also explore whether co-occurring psychiatric disorders, gender, concurrent treatment exposure, trauma history, or impulsivity are predictors of treatment outcome.

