f. Power Analysis: The sample size of 72 was chosen to ensure sufficient power (at least 80%) of a twosided test with level of significance α =0.05 for detecting difference between the two experimental treatments with respect to time to relapse, based on the Cox proportional hazards model. We expect that the nabilone and XR-NTX group will have greater time to relapse than the placebo group. The rate of retention for the placebo group at 12 weeks can be expected to be 15% based on our prior studies. With 36 per arm, we will be able to detect a difference in retention (without relapse) rates between placebo versus nabilone and XR-NTX of approximately 25% (i.e. 15% on placebo vs 39.6% on nabilone and XR-NTX). This corresponds to a hazard ratio of 0.49 (Machin et al. 1997). The proposed sample size will also enable us to estimate the retention rate of the treatment group with a 95% confidence interval, ±15%, in the worst case. The computation above was performed assuming that the covariates (i.e., baseline cannabis use and age) do not have a predictive power. The 25% rate difference is consistent with a medium to large sized effect, which is what we are seeking in this early Phase II trial. This represents an effect that would be clinically meaningful and likely to make a substantial impact on the success of XR-NTX treatment in clinical practice A2. Primary and Secondary Outcome Measures Primary Outcome Measure: (1) Cannabis withdrawal (mood, sleep quality and duration, food intake) (2) Cannabis relapse defined as (1) time to any MJ use as recorded by the timeline follow back method and confirmed by urine metabolite levels, or (2) time to dropout, whichever comes first, and (3) medication compliance (% of pills taken) or time to discontinuation. Participants who relapse will continue in the trial to obtain secondary outcome measures. Secondary Outcome Measures: (1) Abuse liability (medication liking, desire to take again) (2) Cognitive task performance (3) Side effects and tolerability.

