C. DATA MANAGEMENT AND ANALYSIS C1. Data Acquisition and Transmission Research assistants trained in behavioral observation techniques will assist in data collection during laboratory sessions. Subjective responses, performance effects, food intake and sleep will be obtained electronically using our custom-designed software programs. Some data (e.g., sleep questionnaires) will be recorded manually, and then entered into an Excel spreadsheet. C2. Data Entry Methods As noted above, a portion of the data is automated and a portion is recorded on data sheets, and transferred manually to an Excel spreadsheet. C3. Data Analysis Plan Subjective effects, food intake, sleep, and task performance will be analyzed using repeated measures analysis of variance (ANOVA) models with planned comparisons calculated with SUPERANOVA, SPSS or SYSTAT packages. We will use a cluster analysis of peak subjective effects ratings to reduce the overall number of comparisons (Haney et al., 2013a,b). Tests of differences will be based on F-statistics with degrees of freedom corrected, depending on the observed within-subject correlation of the measures, using the method of Huynh and Feldt. Planned contrasts will be single degree of freedom comparisons using the appropriate interaction error term. Results will be considered statistically significant at p < 0.05, using 2- tailed tests. The primary analyses in this study will be on the intent-to-treat (ITT) sample, i.e. on all randomized patients. Cannabis consumption and cannabis abstinence, are assessed repeatedly over time and we will try to collect them at all study assessment points. We will account for unobserved data by examining the primary outcome variables using longitudinal mixed effects models (MEM) (Brown & Prescott, 1999; Diggle, et al., 2002) using PROC GLIMMIX in SAS[®]. MEMs do not require complete measurements data to estimate the outcome variable. The inferences from analyses with missing data are valid provided that they are "missing at random" (Little & Rubin, 2002). 'Missing at random' (i.e the missing mechanism does not depend on the value of the unobserved outcome) is untestable in most medical research and in our study as well. One can assume either parametric or semiparametric models for the missingness that does depend on the unobserved outcome value and do the analysis (Diggle & Kenward, 1994; Kenward, 1998; Liu, et al., 1999; Rotnitzky, et al., 1998; Scharfstein, et al., 1999). Comparison of the inferences from assuming various models for the missingness provides a measure of the validity of the efficacy estimate from the model that assumes missing 'at random'. One can also compute a local sensitivity index which measures the change in the estimated treatment effect in a neighborhood of the 'missing at random' model for missingness (Rotnitzky, et al., 2001). We plan to perform a sensitivity analysis based on these two approaches to assess the effect of the assumption of missing 'at random' on the inference.

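### Model (3), if it governs the clonazepam trial's weekly outcomes, has a random intercept only, so its treatment-by-week and week-12 standard errors are too small when patients' trajectories diverge (minor; secondary outcomes)

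*SAP*

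**What the plan says.** SAP section 3.e.ii, Hypothesis 4, defines model (3) for days of use in each of weeks 1 to 12. It has a linear week effect, a treatment indicator, their product, covariates and an error term, and "sij is a random intercept for subject i". The treatment-by-week product is tested first. If it is significant, "the groups will be compared (using contrast) in the last time point t=12"; otherwise the model is refitted without it and the treatment main effect is tested. Hypotheses 5 to 7 (withdrawal, craving, sleep) reuse the model: "We will first test the interaction effect of group and time as described for Hypothesis 4".

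Sections 3.c and C3 name mixed models in PROC GLIMMIX but give no covariance structure. Their sensitivity analyses concern the missing-at-random assumption only. The one correction for within-patient correlation, Huynh-Feldt in C3, belongs to the repeated-measures ANOVA.

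On the level of the tests, section 3.d sets two-tailed 5% for main effects. In C3, "Results will be considered statistically significant at p < 0.05" follows the ANOVA contrasts. No level is stated for the interaction in model (3).

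On scope, sections 3.b to 3.f describe nabilone/XR-NTX with 36 per arm. The clonazepam text (A2, A4, C3) has 40 per arm and its own outcome list. Protocol Table 3 nevertheless schedules the timeline follow-back, Marijuana Withdrawal Checklist and Marijuana Craving Questionnaire weekly in the clonazepam trial, and model (3) is the only longitudinal mixed model this SAP writes out.

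**The concern.** A random intercept with independent errors assumes that, apart from week-to-week noise, all patients in an arm follow parallel lines. That is unlikely for use days in this design. Patients leave the inpatient unit abstinent, relapse in different weeks, and remain under observation: "Participants who relapse will continue in the trial to obtain secondary outcome measures". Their use therefore climbs at different times, and one intercept per patient cannot describe that.

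When real variation between patients' slopes is left out, it is pooled into the residual and spread over all the weekly values. The analysis then treats patients' slopes as better determined than they are. Both the interaction test and the week-12 contrast depend on those slopes. At stake is whether a reported change in treatment effect over time, or a week-12 difference that follows from it, has the error rate a reader would assume.

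**Working it through.** **Inputs from the documents:** 12 weekly values and a random intercept only (SAP 3.e.ii); 36 or 40 per arm (3.b, A4); 15% event-free on placebo (A4); 60 completers of 80 enrolled (Protocol, Description of Subject Population). **Assumed:** slope SD, intercept SD and use pattern after relapse, since the documents give none. All results are under no treatment effect.

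**1. Interaction, closed form, complete data.** Let r be the slope SD divided by the residual SD. The sum of squares of weeks 1 to 12 about their mean is 12 × (144 − 1)/12 = 143. In units of the residual variance:

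- True variance of a patient's fitted slope: r² + 1/143.
- Variance model (3) assigns: pooled residual/143, with pooled residual = (10 + 1 + 143r²)/11 = 1 + 13r².
- Ratio R = (1 + 143r²)/(1 + 13r²); rejection rate = 2 × [1 − Φ(1.96/√R)].

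| r | R | √R | Rejects |
|---|---|---|---|
| 0 | 1 | 1 | 5.0% |
| 0.03 | 1.1287/1.0117 = 1.116 | 1.056 | 6.4% |
| 0.05 | 1.3575/1.0325 = 1.315 | 1.147 | 8.7% |
| 0.10 | 2.43/1.13 = 2.150 | 1.466 | 18.1% |

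The nominal 5% is reproduced when the model is right. The ratio does not depend on the number per arm.

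**2. Week-12 contrast, taken alone.** The fitted week-12 value is the patient's mean plus 5.5 times the slope, and 5.5²/143 = 0.2115. Take intercept SD equal to residual SD.

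- Slopes acting on centred weeks: true variance 1 + 1/12 + 30.25r² + 0.2115; model variance 1 + 1/12 + 0.2115(1 + 13r²). At r = 0.10 this is 1.597/1.322 = 1.208, which rejects 7.5%.
- Slopes acting on uncentred weeks: true variance 1 + 1/12 + 144r² + 0.2115; model variance 1 + 1/12 + 42.25r² + 0.2115(1 + 13r²). At r = 0.10 this is 2.735/1.745 = 1.567, which rejects 11.7%.

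At r = 0.03 the same formulas give 5.2% and 5.8%. The range for these slopes is therefore about 5-12%.

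**3. Relapse onset, simulated.** Relapse time is exponential with 15% event-free at week 12, the same in both arms, with various assumed use levels afterwards. The interaction rejects about 17-37%. The low end arises when use days vary from week to week, the high end when each patient keeps a fixed level. The week-12 contrast alone rejects about 9-14%. With 25% random dropout, matching 60 of 80 completing, one such scenario moved from 28.7% and 11.4% (interaction, week 12) to 28.9% and 13.4%.

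**4. The sequence as written, simulated.** A false arm difference means a significant interaction with a significant week-12 contrast, or a non-significant interaction with a significant main effect.

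| Truth | Interaction | Week 12 alone | Whole sequence |
|---|---|---|---|
| Model (3) correct | about 5% | about 5% | about 5-6% |
| r = 0.03 to 0.10 | 6-18% | 5-12% | 5-10% |
| Relapse onset | 17-37% | 9-14% | 9-13% |

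The main-effect test rejected 4.5-5.4% throughout with complete data, because it compares patient means.

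**5. After correction.** Random-slope-equivalent tests gave 4.4-5.8% (interaction) and 4.3-5.5% (week 12) with complete data. A small-sample-corrected sandwich with the random intercept gave 4.4-6.5% and 4.3-5.7% under random dropout. The random slope under dropout gave 4.9-6.9% and 4.9-5.6%.

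**The case against.** The strongest objection is applicability. Model (3) sits in text for other drugs and a 72-patient trial. The clonazepam text sends sleep, food intake and subjective effects to an ANOVA with its own correlation correction, and lists neither use days nor craving among its outcomes. This stands: the covariance point is conditional on model (3) being used here. It does not dispose of the matter, because C3 also calls for mixed models without writing one.

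Second, a reader might take the 17-37% as the trial's false-positive rate. The documents do not support that. The interaction is a gatekeeper that selects the comparison to report, and the sequence as a whole runs at about 5-13% in the scenarios examined. At r = 0.03 the sequence inflation is negligible.

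Third, the sizes come from assumed values, and the ranges describe the scenarios run; they are not bounds. The 15% event-free figure counts dropout as an event as well as relapse, whereas the relapse scenario treats every event as an observed relapse. This stands for the size. The direction does not depend on it: any positive slope variance makes R exceed 1.

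Fourth, the 5% level for the interaction is inferred, since 3.d gives it for main effects and C3 for the ANOVA contrasts. That is correct. No other level is offered anywhere.

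**Conclusion.** The point holds in conditional form. Model (3) states no term that would absorb diverging trajectories. If it governs the clonazepam trial's use days, withdrawal checklist and craving scores, its interaction and week-12 standard errors are too small when trajectories diverge. Divergence is likely for use days and less certain for the two scales.

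Under the assumed values, the written sequence yields a false arm difference in about 5-10% for slope SDs of 0.03-0.10 of the residual SD and about 9-13% under relapse onset, against about 5-6% when the model is right. The week-12 rates given on their own are unconditional, whereas the SAP makes that contrast only after a significant interaction.

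A reader might infer that the relapse analysis or the treatment main effect is compromised as well. Neither follows. Time to relapse is analysed by a Cox model that does not use model (3), and the main-effect test stays near 5% with complete data (4.3-6.4% in a check with dropout). The outcomes given to model (3) are secondary in section 3.a.ii, so the severity is minor. The sleep scale named in Hypothesis 7 differs from the one the protocol schedules; that is a separate item.

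**What to change.** 1. State whether model (3) applies to the clonazepam trial, to which outcomes, and at what level the interaction is tested.
2. If it applies, replace the random-intercept-only standard errors in one of two ways:
   - add a random slope for week with Kenward-Roger degrees of freedom, and pre-specify the random-intercept model with small-sample-corrected sandwich standard errors in case of non-convergence; or
   - use the corrected sandwich standard errors throughout.

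Both options came close to 5%. The random slope was checked with a t reference on N − 2 degrees of freedom standing in for Kenward-Roger. The sandwich avoids the convergence risk.

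The cost is a few lines of SAP text and code, plus wider standard errors. With the random slope, the interaction standard error grows by about 6%, 15% and 47% at r = 0.03, 0.05 and 0.10 (the √R column), and by 42-81% in the relapse-onset runs that compared them. The week-12 standard error grows less: at r = 0.10, √1.208 = 1.10 for centred slopes or √1.567 = 1.25 for uncentred slopes, and 17-18% under relapse onset. The order of tests need not change. The correction concerns precision only; it does not alter what a week-12 comparison estimates after four medication-free weeks.

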#### **Background, Significance and Rationale**

#### Background, Significance and Rationale

Cannabis use is increasing and numbers are likely to rise further with legalization (Hasin et al., 2015). Currently, approximately 24% of patients entering treatment for a substance use disorder have cannabis use disorder (CUD; SAMHSA, 2013), yet their outcome is poor (MTPRG, 2004; Budney et al., 2006; Kadden et al., 2007; Levin et al., 2011, 2015). There is a clear need for FDA-approved pharmacological options to improve cannabis treatment outcome.

The purpose of this study is to test the effects of the benzodiazepine, clonazepam, as a potential treatment for CUD. The rationale for testing a benzodiazepine is the following: Cannabis withdrawal is, in part, characterized by symptoms such as anxiety and disordered sleeping (Haney et al., 1999, 2005; Budney et al., 2004), and clonazepam is efficacious and used therapeutically to treat both of these symptoms. Although benzodiazepines have the potential for abuse, clonazepam has a long half-life and is less reinforcing that fast-onset benzodiazepines (alprazolam, lorazepam) so was selected to be a time-limited treatment to facilitate the transition from regular cannabis use to abstinence.

Nonetheless, clonazepam is a controlled substance, and its administration to patients with a substance use disorder requires careful monitoring and minimization of the potential risks for misuse and physiological dependence. During the inpatient study period, study medication will be distributed on a single dose basis. During the outpatient period, study medication (clonazepam vs. placebo), will be distributed at weekly intervals and pill counts and biological measures of medication compliance (e.g., quantitative riboflavin) will be performed. The overall time period of potential exposure to clonazepam will be 8 weeks, with a 4 week time medication-free observation period following taper and discontinuation of study medication. These study features should minimize the risk of exposing individuals with CUD to clonazepam.

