symptoms emerge. It is unlikely that the length of time participants are exposed to clonazepam during the protocol will result in the development of physiological dependence that makes discontinuation difficult. However, there may be cases where participants due experience difficulty with the length of the taper schedule. If clinically significant withdrawal symptoms emerge during the taper, the taper may be extended for a second week based on clinical judgment by the study psychiatrist.

We will evaluate the adequacy of the double-blind by asking patients which treatment drug they think they are receiving. The blinded nurse will also be asked to report which drug s/he thinks each patient is taking. The research staff that administers medication and/or conducts interviews and assessments will be blind to medication condition, urine toxicology results, and medication blood levels during the course of the 12-week trial. The non-blinded pharmacist will be the only ones who have access to this information during the trial. However, a sealed envelope will be kept in the locked office if the Principal Investigator needs to break the blind in an emergency situation. At the completion of the 12 week trial, or at the conclusion of the patient's involvement in the trial (if they do not complete all 12 weeks), patient will learn their treatment assignment.

The medication capsules will contain riboflavin. This non-harmful substance will allow the clinic to verify that the study medication is being taken correctly and absorbed by the body. The urine samples obtained twice per week will be examined for riboflavin. In addition, folic acid in the form of a 1mg "pill" will be added to all placebo capsules in an attempt to improve the blind. The patient will receive up to 2mg of folic acid daily. Patients will receive medication in non-childproof packaging.

*Medication Adherence Enhancement*: We will use a combination of the quantitative fluorometric riboflavin determination method developed by our research group (Herron et al. 2013), timeline followback interview, and pill count with a weekly financial incentive (\$10) for medication bottle return to both enhance and measure medication adherence. Note, participants will be instructed to take their morning capsules and come to the clinic within 6-8 hours to ensure that riboflavin levels will be detectable.

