#### **Outpatient Study Assessments**

Adverse Effects measures: The Systematic Assessment for Treatment and Emergent Events (SAFTEE; Johnson et al. 2005) adapted for clonazepam will be performed weekly to identify adverse symptoms. Benzodiazepine withdrawal measure: The Clinical Institute Withdrawal Assessment-Benzodiazepines (CIWA-B)(Busto, 1989) is a 22-item scale to assess the degree of benzodiazepine withdrawal. Cannabis Craving measure: The Marijuana Craving Questionnaire (MCQ) is a 47-item instrument (Heishman et al. 2001).

Columbia Suicide Severity Rating Scale: Will be used to monitor suicidality at baseline and twice a month during the study period.

Medical Evaluation and Monitoring: A medical history and physical exam will be performed during screening. Serum pregnancy testing will be performed during screening and urine pregnancy testing will be performed monthly during the study. Complete blood count, electrolyte, urinalysis and liver function tests will be performed during screening and monthly during the study. Height and weight will be measured and baseline body mass index (BMI) calculated during screening. Temperature, pulse, blood pressure, and weight will be measured at every study visit.

Cannabis Use Outcome measures: Cannabis use will be recorded by the timeline followback (TLFB) method (Litten and Allen 1992) modified for cannabis and confirmed by creatinine-normalized quantitative urine THC levels. Other substance (including nicotine and alcohol) use self-report data will also be gathered during the TLFB interview. Urine samples for quantitative urine THC levels and creatinine will be collected under directly-observed conditions during screening and at each study visit (twice weekly). Creatinine levels can be used to control for urine concentration variability and screen for adulterated samples. Creatinine-corrected quantitative urine THC levels will then be used to confirm self-reported cannabis use, using a method similar to that described by Preston et al. (Preston et al. 1997) for cocaine dependence, where an obvious pattern of new use (i.e., level more than doubles in the past two days) overrides a self-report of no use.

Cannabis Withdrawal measure: We will use the 22-item version of the Marijuana Withdrawal Checklist (MWC; Budney et al. 1999) that measures subject-rated severity as the primary outcome measure of withdrawal.

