*Clinical Status*: The Clinical Global Impression Scale-Observer (CGI; Guy 1976) will be used to measure the overall clinical status of the participant as well change from baseline in symptom severity. The Clinical Global Impression-Self (CGI-S) is a two-item scale that asks the subject to rate his or her current level of symptoms and estimate changes from baseline (Guy 1976).

Cognitive, Behavioral and Impulsivity Measures: A series of cognitive and behavioral measures will be performed at baseline, end of active medication treatment (week 8), and end of the observation period (week 12), to explore potential therapeutic mechanisms of action of the medication treatment.

Concurrent Treatment measure: The Modified Treatment Services Review assesses the past-week exposure to health care, psychiatric, or substance use disorder treatment (McLellan et al. 1992).

Medication Adherence measures: The Structured Pill Count Interview is a timeline followback assessment of study medication compliance accounting for each dose of prescribed study medication. Fluorometric detection of a urinary riboflavin concentration (Herron et al. 2013) will be used as a biological method to determine compliance with study medication.

Anxiety measure: A structured-interview version of the Hamilton Anxiety Scale (HAM-A; Hamilton 1959) will be used to assess mood and anxiety symptoms at baseline and changes associated with treatment.

Psychiatric Evaluation and Diagnosis: The MINI International Neuropsychiatric Interview will be performed during screening as part of a complete psychiatric diagnostic assessment.

Sleep measure: The Pittsburgh Sleep Quality Index Scale (PSQI; Buysse 1989) will be the primary outcome of sleep quality and length.

Please attach copies, unless standard instruments are used outpatient study assessments 5-24-16.pdf

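### If SAP section 3 governs the clonazepam trial, Hypotheses 4–7 fit one straight line across a planned drug stop, and neither branch of the testing rule estimates the on-drug effect without bias

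*SAP*

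**What the plan says.** SAP 3.e.ii, Hypothesis 4, analyses days of cannabis use per week with a random-intercept mixed model, numbered (3). It contains treatment, one linear term in week for t = 1 to 12, and their product. If the product is significant, the arms get their own slopes ("the effect of time will be estimated for each group separately"). The only between-arm comparison named after that step is at week 12: "the groups will be compared (using contrast) in the last time point t=12". If the product is not significant, it is dropped and the treatment main effect over all twelve weeks is tested. For withdrawal, craving and sleep the SAP says "To test the secondary hypotheses 5, 6, and 7 we will use the same model as in (3"). Hypothesis 2 tests abstinence "during the final 2 weeks of study (weeks 11 and 12").

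The protocol's dosing table (Table 2) tapers study drug over days 50–56 and lists none for days 57–84. The Background describes eight weeks of possible exposure, "with a 4 week time medication-free observation period following taper and discontinuation of study medication". Under Medication Taper in Study Procedures, "the taper may be extended for a second week based on clinical judgment by the study psychiatrist" if withdrawal symptoms emerge.

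For cognitive measures the protocol does separate the two periods: they are taken at baseline, "end of active medication treatment (week 8), and end of the observation period (week 12"). The weekly Marijuana Withdrawal Checklist is described, under Outpatient Study Assessments, as the scale "that measures subject-rated severity as the primary outcome measure of withdrawal".

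Section 3 names nabilone/XR-NTX and 72 patients, although it is filed under this study's number and title. The clonazepam text (A2, A4, C3) mentions mixed models but gives no time structure, week or contrast for them.

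**The concern.** A treatment that works while taken and stops working when withdrawn produces a step in the group difference at about week 8. Model (3) can represent only a straight line. The step tilts that line and so tends to make the interaction significant. The rule then moves the group comparison to week 12, when nobody is scheduled to be on drug. If the interaction is missed, the fallback averages weeks with drug and weeks without it.

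What is at stake is the answer to a basic question for this design: how large was the difference in weekly use, withdrawal, craving or sleep while patients took clonazepam? The data to answer it are collected, but the plan names no estimate that does so.

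**Working it through.** **Plan's own figure.** The SAP gives no power or sample size for Hypotheses 2–7. Its only clonazepam sample size, in A4, reproduces: HR = ln(0.4181)/ln(0.15) = 0.4597; Freedman events = (1.96 + 0.8416)² × (1.4597/0.5403)² ≈ 57.28; N = 57.28/(1 − (0.15 + 0.4181)/2) = 80.0. This point does not rest on an error there. I take 40 per arm from it.

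**Timing (protocol Table 2).** The last scheduled dose is on day 56. Week 12 is days 78–84, which is 22–28 days later. Weeks 11–12 are days 71–84, which is 15–28 days later. With a second taper week (to day 63), weeks 11–12 still begin 8 days after the last dose.

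**What model (3) estimates.** With complete, balanced data and a random intercept, the fitted group difference is the least-squares line through the weekly true differences d(t). The mean week is 6.5 and Σ(t − 6.5)² = 143. So slope = Σ(t − 6.5)d(t)/143, main effect = mean of d(t), and fitted week-12 value = mean + 5.5 × slope.

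- Effect -1 in weeks 1–8, then 0: mean = -8/12 = -0.667; slope = 16/143 = 0.112; week 12 = -0.667 + 0.615 = -0.05.
- Effect -1 in weeks 2–8, then 0 (week 1 is mostly inpatient): mean = -7/12 = -0.583; slope = 10.5/143 = 0.073; week 12 = -0.583 + 0.404 = -0.18.
- Effect -1 in weeks 2–9 (extended taper): mean = -8/12 = -0.667; slope = 8/143 = 0.056; week 12 = -0.667 + 0.308 = -0.36.
- Effect -1 in weeks 1–8, half kept afterwards: this is the average of the first case and full persistence, so week 12 = (-0.051 − 1)/2 = -0.53 and mean = (-0.667 − 1)/2 = -0.83.
- Effect -1 throughout: week 12 = -1 and mean = -1.

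The line does not recover the on-drug value even if read earlier. In the first case it gives -1.28 at week 1 and -0.50 at week 8, against a true -1 at both.

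**How often each test is significant (assumed inputs).** The documents give no SDs or effect size for these outcomes. Take a benefit of 1 day/week in weeks 2–8 only, within- and between-subject SD 1.5, 40 per arm, complete data:

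- Interaction: SE = √(2 × 2.25/(40 × 143)) = 0.0280; z = 0.0734/0.0280 = 2.62; power Φ(0.66) ≈ 0.74 (simulated 0.731).
- Weeks 2–7 contrast: SE = √((2/40)(2.25 + 2.25/6)) = 0.362; z = 2.76; power Φ(0.80) ≈ 0.79 (simulated 0.775).
- The rule's follow-up comparison (simulated, two-sided): week-12 branch 0.036, main-effect branch 0.096, either 0.131.
- Interaction or fallback main effect: 0.731 + 0.096 = 0.827.

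The ranges below cover within- and between-subject SDs of 1 to 2 days/week and effects confined to weeks 1–8, 2–8 or 2–7. The interaction is significant in about 49–100% of trials. The follow-up comparison favours drug in about 3–31%, against 53–98% for a weeks 2–7 contrast. An interaction or fallback main effect is significant in about 60–100%. If the benefit persists fully, the present rule detects it in 55–99% and the weeks 2–7 contrast in 53–98%.

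**The case against.** **Section 3 may not apply.** It names other drugs and another sample size, and the outcomes in A2 match the protocol's own list, which has no weeks 11–12 abstinence test and no week-12 contrast. This stands, and it is why the point is conditional. Applicability cannot be excluded either, because the section carries this study's number and title.

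**A reader might infer that a benefit ending with the drug would be reported as no treatment difference.** The documents do not support that. Hypothesis 4 treats a significant interaction as a finding that the groups differ over time, and it then estimates each group's slope. With the assumed inputs above, some treatment term is significant in most trials, and a significant interaction would point towards early benefit. What is missing is the size of the on-drug effect.

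**A reader might also infer that the fitted week-12 difference would have the wrong sign.** That needs a benefit confined to the first weeks. For weeks 1–4 only, the value is -0.333 + 5.5 × 0.112 = +0.28. The documents give no such duration, and in simulation this value was significantly adverse in only 8–19% of trials.

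**Off-drug endpoints are legitimate.** Clonazepam is presented as a time-limited treatment, so weeks 11–12 abstinence is a proper durability target. The fitted week-12 value is also fairly close to the true off-drug difference in these scenarios. Both stand; neither supplies an on-drug estimate.

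**On-drug evidence exists elsewhere.** The inpatient withdrawal analysis covers days 2–5, and the Cox analysis of relapse uses on-drug time from day 6. This stands. However, the first ends before the outpatient weeks, and the second gives one coefficient pooled over both periods. Neither estimates weekly use, withdrawal, craving or sleep during outpatient treatment. The checklist's description as primary for withdrawal appears among the outpatient assessments and does not by itself redefine the trial's primary outcome.

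**Conclusion.** The point holds in conditional form and is worth correcting before analysis. If section 3 governs, model (3) draws one line through a planned discontinuation. Its only contrast after a significant interaction is off drug, and its fallback mixes the two periods. For a true on-drug effect of -1 that ends with the drug, the week-12 contrast returns -0.05 to -0.18 and the fallback -0.67 to -0.58.

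These projections depend only on the assumed shape of the effect over time and on complete data. The power figures depend on assumed SDs and effect size and are illustrative. If the effect persists fully from week 1, there is no bias. Hypothesis 2 is not at fault as a durability endpoint, but taken alone it cannot distinguish a treatment that never worked from one whose effect wore off.

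**What to change.** 1. State whether Hypotheses 2–7 apply to clonazepam. If they do not, this point falls away as written, and the mixed model in C3 still needs a stated time structure and contrast.
2. If they do, replace the linear time term and the sole week-12 contrast in model (3) with week, or period, as a category.
3. Pre-specify one on-drug contrast (for example weeks 2–7) and one off-drug contrast (for example weeks 10–12, which allows for a second taper week) for each longitudinal outcome.
4. Keep weeks 11–12 abstinence as the durability endpoint, and say in its interpretation that it is measured off drug.

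The cost is SAP wording. The Timeline Follow-Back, withdrawal checklist, craving questionnaire and PSQI are already scheduled weekly in protocol Table 3. The downsides are one extra contrast per longitudinal outcome and somewhat less power for the off-drug contrast if the benefit fully persists: 48–97% against 55–99% for the present rule, under the SDs assumed above.

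The relapse definition, the choice of sleep scale and the week to which the 15% in A4 refers are separate questions and are not part of this point.
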